In order to fully elucidate the analgesic and side effect properties of hydromorphone for cesarean delivery, a prospective randomized, double blind study comparing morphine and hydromorphone is necessary. We need to understand whether hydromorphone is as effective as morphine for analgesia after cesarean section, and whether it is associated with fewer or more side effects. The results of the study will allow providers to make educated decisions to better care for their patient.

 MOUNT SINAI SCHOOL OF MEDICINE	Protocol Title:	
	Principal Investigator:	
	Primary Contact Name/Contact Info	
	Date Revised:	
	Study Number:	

1) Objectives

The purpose of this study is to determine whether there is a difference in analgesic effect of intrathecal morphine and hydromorphone for cesarean section.

2) Background

Opioids are often administered intrathecally for cesarean section for post-operative analgesia. Opioids act in the substantia gelatinosa of the dorsal horn of the spinal cord. When activated, these receptors inhibit the release of excitatory neurotransmitters within the spinal cord. The most important factor to consider when administering intrathecal opioids is the lipid solubility.

Lipophilic opioids, such as fentanyl, enter the spinal cord rapidly, quickly diffuse across the dura and into the epidural fat and are rapidly cleared into the systemic circulation. Due to the rapid distribution, lipophilic opioids have limited spread within the cerebrospinal fluid (CSF). As a result of these features, lipophilic opioids result in a rapid onset and short duration of action. Fentanyl, for example, has an onset of action of 5-10 minutes and duration of 2-4 hours.

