	Primary Contact Name/Contact Info	
	Date Revised:	
	Study Number:	

The dermatomal level of anesthesia will be assessed every 2 minutes until the anesthetic level reaches thoracic level 4 (t-4). We will test for adequate level of anesthesia with a needle testing for the sensation of a pin prick. .

Patient satisfaction will be recorded at the end of the procedure. Patients will be asked to rate their experience on a 1-5 scale as follows. 1-completely dissatisfied, 2-partially dissatisfied, 3-neutral, 4-partially satisfied, 5-completely satisfied.

All patients will have the same post op pain orders as is standard on the labor floor. These include ketorolac 30mg IV every 6 hours. In addition to this, every patient in this study will be given an IV fentanyl PCA (patient controlled analgesia) pump. The settings of the pump will be basal rate of 0, bolus rate of 15mcg, and a lock out of every 8 minutes. This allows a maximum hourly dose of 105mcg. The PCA pumps record how often the patient requested additional analgesia and how much total fentanyl the patient received per hour. The pumps will be queried at the end of 24 hours to record total fentanyl dose can record the total medication administered per hour over a 24 hour period.

The patients will then be followed hourly for the first 4 hours by the investigating team. Pain scores will be obtained using the verbal response scale (VRS). The VRS scale is measured using a score of 0 as no pain and 10 as the worst pain. The presence of nausea and pruritus will also be assessed at these time points. The patients will then be visited again at 6hrs, 12 hrs, and 24 hrs. At these time points, the patients will be asked for pain scores, presence of nausea, vomiting and pruritus.

At 24 hrs, the patients will be evaluated for overall satisfaction with pain control and their anesthetic experience.

a) Recruitment Methods

Every patient that presents for primary elective cesarean section will be a potential candidate for this study. After admission to the labor and delivery floor, the patient will be approached by a member of the investigating team. These patients will be informed about the trial and consent will be obtained. If the patient does not wish to take place in the trial, she will receive standard anesthetic care.

 MOUNT SINAI SCHOOL OF MEDICINE	Protocol Title:	
	Principal Investigator:	
	Primary Contact Name/Contact Info	
	Date Revised:	
	Study Number:	

b) Inclusion and Exclusion Criteria

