Inclusion Criteria for this study:

Elective primary cesarean section; Females age 18-40

Exclusion Criteria:

Emergency cesarean section; Anesthetic other than spinal; History of chronic pain or pre-op opioid use; Allergy to morphine or hydromorphone; BMI>40

c) Number of Subjects

Since there are no prior studies comparing Duramorph to hydromorphone for postoperative analgesia we cannot perform a power analysis to determine the number of patients required. We propose to enroll 20 patients, 10 per group, in a blinded fashion and collect our data as described above. We will then perform an interim analysis of the data to see how much fentanyl is being used in the hydromorphone and morphine group. At that point we will determine the total number of patients required and inform the IRB and update the protocol accordingly. We will not change the protocol in any way after analyzing the data.

d) Study Timelines

Each individual subject will be followed for 24 hours after cesarean section.

We anticipate that we will enroll all subjects within 1 year.

We estimate that this study will be completed 6 months after enrollment of all subjects.

e) Study Endpoints

Each patient will receive a fentanyl pca (patient controlled analgesia) pump in the post anesthesia care unit (pacu). The primary outcome is total dose of fentanyl pca used in 24 hours. This will be a marker for supplemental analgesia needed after the cesarean delivery.

Secondary outcomes include:

1. Time to initial use of pca. We want to understand when the hydromorphone and morphine group will require the first supplemental analgesic.

 MOUNT SINAI SCHOOL OF MEDICINE	Protocol Title:	
	Principal Investigator:	
	Primary Contact Name/Contact Info	
	Date Revised:	
	Study Number:	

2. Time frame of most frequent use of pca. When does each group use the pca most frequently? Between 1-4 hrs, 4-6 hrs, 6-12 hrs, 12-24 hrs? This will help us understand the duration of analgesic effect between hydromorphone and morphine.
3. Pain scores in both groups between the above time frames.
4. Patient satisfaction scores in the above time frames.
5. Assessment of nausea and vomiting and pruritus in the above time frames. This will help us understand the onset and incidence of these side effects among the two groups.

f) Procedures Involved in the Human Research

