17) Sharing of Results with Subjects

Results will not be shared with the patients or their obstetricians.

 MOUNT SINAI SCHOOL OF MEDICINE	Protocol Title:	
	Principal Investigator:	
	Primary Contact Name/Contact Info	
	Date Revised:	
	Study Number:	

18) IRB Review History

N/A

19) Control of Drugs, Biologics, or Devices

Note: The IDS has its own forms that must be completed and a review process that must be followed before the IDS representative will sign off on Appendix B for submission to the PPHS.

The Mount Sinai Labor and Delivery Unit utilizes a Pyxis machine, which stores and dispenses controlled substances. The pyxis is accessed by passcode and fingerprint. Currently the morphine used for cesarean section is stored in the pyxis and is accessed by identifying the patient and withdrawing the drug. The Pyxis records who took out the medication and the time of withdrawal. The hydromorphone will be stored in this secure pyxis machine as well.

References:

2. Rauch, E. "Intrathecal Hydromorphone for Postoperative Analgesia After Cesarean Delivery: A Retrospective Study". AANA Journal. 2012 Aug;80(4 Suppl):S25-32
3. Halpern, S.H et al. "Epidural Morphine vs. Hydromorphone in post-cesarean section patients". Canadian Journal of Anesthesia. 1996; 43(6):595-598.

Statistical plan

Categorical variables were tested via chi-square test, while continuous variables were tested via t-test, paired t-test, Wilcoxon rank sum test, or Mann-Whitney U test where applicable.

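### Side effects are assessed in four time frames with no overall comparison per symptom, so separate unadjusted tests could yield a chance answer to a stated trial question

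*Combined protocol and SAP*

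**What the plan says.** The Brief Summary of Research gives side effects as one of the things the trial must settle: "whether it is associated with fewer or more side effects".

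Section 5e (Study Endpoints) takes this up as secondary outcome 5: "Assessment of nausea and vomiting and pruritus in the above time frames". The frames are set under outcome 2: "Between 1-4 hrs, 4-6 hrs, 6-12 hrs, 12-24 hrs". The stated use of outcome 5 is "This will help us understand the onset and incidence of these side effects among the two groups". Outcome 3 handles pain in the same way: "Pain scores in both groups between the above time frames".

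Section 5 (Study Design) sets the readings: "The patients will then be followed hourly for the first 4 hours by the investigating team", then visits at 6, 12 and 24 hours. Nausea and pruritus are named at the hourly visits; vomiting is added only from 6 hours. During surgery, nausea and vomiting, and pruritus, are also recorded at 5-minute intervals.

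The Statistical plan is a single sentence. For symptoms recorded as present or absent, the relevant part is "Categorical variables were tested via chi-square test". Pain scores fall under its other part, which offers a choice among the t-test, the paired t-test and two names for the rank-based test. It gives no significance level, main frame, overall test per symptom, method for repeated readings or multiplicity rule.

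**The concern.** The trial asks one question about side effects, but the endpoint is divided into symptom-by-frame cells and no cell or summary is named as the answer. With the tests listed, the natural way to carry out outcome 5 is a chi-square test in each cell. Nothing in the plan would then stop one frame below 0.05 from being reported as the side-effect result. At stake is an erroneous statement, in either direction, on a comparison the protocol presents as a reason for the trial.

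There is also a gap over repeated readings. If each frame includes its upper limit, the 1-4 h frame holds four readings per patient (hours 1, 2, 3 and 4) and each later frame holds one. The listed tests for comparing the arms need one independent value per patient, and no rule says how four readings become one.

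**Working it through.** The documents give no error rate to reproduce, so the size has to be worked out from stated inputs and labelled assumptions.

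**From the documents.** Four frames (section 5e). Two symptoms if nausea and vomiting are one item, three if separate. Seven postoperative visits (section 5). Total of 50 patients (section 4), although section 5c leaves the final number to be set after 20.

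**Assumed.** Two-sided 0.05 per test; no true difference between arms; 25 per arm where a sample size is needed; correlation between frames from 0 to 0.7 and between symptoms from 0 to 0.3.

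**Number of tests, k.** Combined: 2 × 4 = 8. Separate: 3 × 4 = 12, or 11 if the 1-4 h vomiting cell is dropped because no vomiting reading is named at the hourly visits.

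**Independent tests.** Any false difference: 1 − 0.95^k. A false result favouring hydromorphone: 1 − 0.975^k, since only half of each two-sided test counts.

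| k | Either direction | Fewer only |
|---|---|---|
| 8 | 1 − 0.663 = 33.7% | 1 − 0.817 = 18.3% |
| 11 | 1 − 0.569 = 43.1% | 1 − 0.757 = 24.3% |
| 12 | 1 − 0.540 = 46.0% | 1 − 0.738 = 26.2% |

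**Correlated tests** (simulated normal test statistics; 11 tests not run separately).

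| Correlation: frames, symptoms | 8 tests: either / fewer | 12 tests: either / fewer |
|---|---|---|
| 0.3, 0.2 | 31.5% / 16.4% | 43.0% / 22.9% |
| 0.5, 0.3 | 28.1% / 14.3% | 38.2% / 19.9% |
| 0.7, 0.3 | 23.7% / 12.0% | 32.7% / 16.6% |

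The ranges are therefore about 24-46% in either direction and 12-26% for fewer only.

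**Effect of the chi-square itself.** This was simulated at 25 per arm with illustrative rates of 30% nausea, 10% vomiting and 50% pruritus. The uncorrected test has a per-test size of about 5.6-6.0%. It gives 33-39% (8 tests) or 44-50% (12 tests) in either direction, and 17-22% or 23-29% for fewer only. With continuity correction the figures fall to 17-21% and 9-11%. The plan does not say which form would be used.

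**Pooling the four hourly pain scores (conditional).** If 4 readings per patient with within-patient correlation ρ were treated as independent, the true variance of an arm mean would be D = 1 + 3ρ times the assumed one. The actual size of a nominal 5% test is 2[1 − Φ(1.96/√D)].

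- ρ = 0.3: D = 1.9, 1.96/√1.9 = 1.42, size 15.5% (simulated 15.8%)
- ρ = 0.5: D = 2.5, 1.96/√2.5 = 1.24, size 21.5% (simulated 22.4%)
- ρ = 0.7: D = 3.1, 1.96/√3.1 = 1.11, size 26.6% (simulated 27.4%)

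**With one main test per symptom.** Unadjusted: 1 − 0.95² = 9.75% for two symptoms, 1 − 0.95³ = 14.3% for three. With Bonferroni: 4.9% in both cases. Holm also keeps the family at or below 5%.

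**The case against.** These are secondary outcomes behind one named primary, 24-hour fentanyl use. Leaving secondaries unadjusted is common when they are labelled exploratory. Outcome 5 speaks of understanding onset and incidence, which can be read as descriptive, and incidence leaves room for a per-patient 24-hour chi-square. The protocol nowhere says that each frame will be tested or what result would support a claim. All of this is fair, and it is why the figures above are conditional on frame-by-frame testing. It does not close the gap: the outcomes are not labelled descriptive, and the overall comparison is not named.

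Three stronger readings are tempting, and the documents do not support them.

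- A reader might infer that a false finding of fewer side effects has a one-in-three or higher chance. The 34% and 46% count differences in either direction under independence. The one-directional chance is 18-26% under independence and 12-17% with the stronger correlations.
- A reader might add the four pain comparisons and quote 1 − 0.95^16 = 56%. Pain scores cannot support a side-effect claim, so they do not belong in that count.
- A reader might infer that the hourly readings will be pooled as independent. No section says so; the plan is silent on how they will be combined.

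**Conclusion.** The concern holds in a limited form. The plan sets a side-effect question and gives no overall per-patient comparison to answer it. With the listed tests applied in each frame at an assumed two-sided 5%, the chance of at least one false side-effect difference is about 24-46%. The chance of a false finding of fewer side effects is about 12-26%, against 2.5% in that direction for a single test. Significance level and correlations are assumptions. The upper ends are not strict bounds, since an uncorrected chi-square at 25 per arm runs slightly above them; a continuity-corrected one runs well below.

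The 16-27% error for pooled readings is a separate, conditional point. It applies to a t-test on pain at an assumed 25 per arm, not to the side-effect question. The matter is worth correcting but does not touch the primary outcome.

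**What to change.** Add to the Statistical plan:

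- **Side effects.** For each symptom, one between-arm comparison of any occurrence at the postoperative readings to 24 h, one value per patient. Apply Holm adjustment across symptoms if a side-effect claim is to be made. State whether nausea and vomiting are one item or two; if two, state whether vomiting is recorded at the hourly visits.
- **Intraoperative readings.** Exclude the 5-minute readings from this comparison. Section 5 lists nausea and vomiting as symptoms of hypotension, so including them would change what the endpoint measures.
- **Pain.** One time-weighted mean over 24 h per patient and one unpaired test.
- **Time frames.** Reduce each frame to one value per patient and report the four as estimates with confidence intervals, to describe onset without significance claims.

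The cost is a few lines of text and no new data. The downside is that a p-value from a single frame can no longer be claimed as a finding.
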